4.3.3 Criteria for dose modifications, treatment interruption and treatment discontinuation

For patients who do not tolerate the protocol-specified dosing schedule, dose adjustments are permitted in order to allow the patients to continue the treatment with the study drug.

[figure not shown]
4.3.3.1 Dose modification criteria in *Part A*

In the Cycle 1 of *Part A* dose modifications will not be allowed. Patients receiving subsequent cycles of treatment in *Part A* may have up to two dose modifications for drug related DLT's (see [paragraph 4.1.1.1](#) for the DLT definition). The first dose modification should be one dose level below the current dose, the second modification should be two dose levels below. Study drug may be resumed at lower dose level once the event resolves to at least grade 1 or baseline values. If toxicities meeting modification criteria occur after the second dose reduction, therapy must be discontinued. Figure 1 outlines the dose modifications scheme for all DLs of Givinostat monotherapy, with exception of DL0 (i.e. 50 b.i.d.) and DL1 (i.e. 100 mg b.i.d.) represented by Figures 2 and 3, respectively. **Patients with unresolved toxicities lasting 2 weeks or longer will not be permitted to continue on study.**

Patients experiencing Grade 3 or 4 unmanageable toxicity will require immediate dose interruption and notification to the Sponsor. Treatment for each new cycle will be delayed until dose limiting toxicities that are clearly not related to disease progression have resolved to at least Grade 1 or the patient's baseline.

[figure not shown]

Figure 1 - Criteria for dose modifications

[figure not shown]

DLT is a Dose Limiting Toxicity. DL_x represents a Dose Level with the exception of DL_0 (i.e. 50 mg b.i.d.) and DL_1 (i.e. 100 mg b.i.d.), represented by Figures 2 and 3, respectively. DL_{x-1} represents the next lower Dose Level (first dose reduction). DL_{x-2} represents the next lower dose level after a first dose reduction (second dose reduction). Grade ≤ 1 represents the severity of AE.

Figure 2 - Criteria for dose modifications for patients treated in DL_0

DLT is a Dose Limiting Toxicity. Grade ≤ 1 represents the severity of AE.

**Figure 3 - Criteria for dose modifications for patients treated in DL1**

DLT is a Dose Limiting Toxicity. Grade ≤ 1 represents the severity of AE.

4.3.3.2 Dose modification criteria in *Part B*

Dose adjustments are permitted for patients who do not tolerate the protocol-specified dosing schedule, in order to allow to these patients to continue the treatment with Givinostat. The guidelines described here below (i.e. see [paragraph 3.3.3.2.1](#) and [paragraph 3.3.3.2.2](#)) need to be followed. The objective of the Givinostat dose adjustment rules described below is to optimize the response for each individual patient, avoiding specific drug-related toxicities. Therefore, dose reductions or interruptions will be mandatory for specific toxicities (see [paragraph 3.3.3.2.1](#)) and dose increases after an initial dose reduction will be allowed in the case of inadequate efficacy at the reduced dosage in absence of specific toxicities (see [paragraph 3.3.3.2.2](#)).

The severity of the above mentioned events will be graded according to NCI Common Terminology Criteria for AE (CTCAE v. 4.03, 14th June 2010).

Each dose modification has to be recorded on the CRF.

Of note, the dose modification criteria described in this paragraph (i.e. see [paragraph 3.3.3.2.1](#) and [paragraph 3.3.3.2.2](#) for details) will be followed also by patients initially dosed at lower dose levels in **Part A** that, after the definition of MTD, are allowed to escalate their Givinostat dose to the MTD for the remainder part of the study (**Part A**) at the discretion of the Investigator **and** after written authorization of Italfarmaco S.p.A..

4.3.3.2.1 Dose adjustments for safety reasons in **Part B**

In **Part B**, the initial dose of Givinostat will be the MTD defined in **Part A** (i.e. 100 mg b.i.d.).

Based on evaluations performed as part of the visit procedures of the Day 28 of each Cycle up to the Cycle 5 (i.e. Cycle 1 Day 28, Cycle 2 Day 28, Cycle 3 Day 28, Cycle 4 Day 28, Cycle 5 Day 28) and/or in any necessary additional study visit, the Givinostat doses **have to be decreased** in case of the occurrence of at least one of the toxicities described in the Table 3.

The objective of these guidelines is to consider the patient's data, prior clinico-haematological response and dose tolerability, in order to achieve an optimized dose for each individual patient, or a balancing between the tolerable dose and the clinico-haematological response, that also take into account the natural course of the disease.

Reductions in Givinostat total daily dose for patients that meet dose reduction criteria (see Table 3 for details) will be achieved by adjusting the morning and evening administered dose level, since the total daily dose is equally divided between the morning and evening administration.

Table 3 - Dose reduction rules in *Part B*

Observed values/data	Action

Grade 1 thrombocytopenia (i.e. PLTs count < local LLN but $\geq 75 \times 10^9/L$)
	
Total daily dose must be reduced of 50 mg/die:
 
 For patients that are receiving the daily dose of 100 mg b.i.d., daily dose must be reduced to 75 mg b.i.d. For patients that are receiving a reduced daily dose of 75 mg b.i.d. or 50 mg b.i.d., daily dose must be evaluated based on the Investigator's decision and after discussion with the Sponsor's representative(s).

Grade 2 thrombocytopenia (i.e. PLTs count < $75 \times 10^9/L$ but $\geq 50 \times 10^9/L$) or Grade 2 anemia (i.e. Hb value < 10 g/dL but ≥ 8 g/dL) or Grade ≥ 3 non-haematological toxicities with exception of: a) Grade 3 diarrhoea without adequate supportive care lasting less than 3 days, and b) Grade 3 nausea or vomiting without adequate supportive care lasting less than 3 days.
	
Total daily dose must be reduced of 50 or 100 mg/die, based on the Investigator's decision and after discussion with the Sponsor's representative(s):
 
 For patients that are receiving the daily dose of 100 mg b.i.d., daily dose should be reduced to 75 mg b.i.d. or 50 mg b.i.d., based on the Investigator's decision and after discussion with the Sponsor's representative(s). For patients that are receiving a reduced daily dose of 75 mg b.i.d. or 50 mg b.i.d., daily dose must be evaluated based on the Investigator's decision and after discussion with the Sponsor's representative(s).

Grade 3 thrombocytopenia (i.e. PLTs count < $50 \times 10^9/L$ but $\geq 25 \times 10^9/L$) or Grade 3 anemia (i.e. Hb value < 8 g/dL; transfusion indicated) or Grade 3 febrile neutropenia (i.e. ANC < $1.0 \times 10^9/L$ with a single temperature of $> 38.3^\circ C / 101^\circ F$, or a sustained temperature $\geq 38^\circ C / 100.4^\circ F$ for more than one hour)
	
Immediate temporary discontinuation of the treatment with Givinostat.
 
The treatment will be interrupted for at least one week. Anyway, the treatment for each new cycle will be delayed until the observed toxicity that is clearly not related to disease progression, has resolved to at least Grade 1 or the patient's baseline value.
 
Daily dose has to be restarted at 75 mg b.i.d. or 50 mg b.i.d., based on the Investigator's decision and after discussion with the Sponsor's representative(s).
 
Patients with unresolved toxicities lasting 4 weeks or longer will not be permitted to continue on study.

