**Table 3 - Dose reduction rules in Part B (continue)**

Observed values/data	Action
Grade 4 thrombocytopenia (i.e. PLTs count $\leq 25 \times 10^9/L$) or Grade 4 anemia (i.e. life-threatening consequences; urgent intervention indicated) or Grade 4 febrile neutropenia (i.e. life-threatening consequences; urgent intervention indicated) or Grade ≥ 3 unmanageable toxicity	
Immediate temporary discontinuation of the treatment with Givinostat.
 
The treatment will be interrupted for at least one week. Anyway, the treatment for each new cycle will be delayed until the observed toxicity that is clearly not related to disease progression, has resolved to at least Grade 1 or the patient's baseline value.
 
The continuation of the study - and the study drug dosage - should be evaluated based on the Investigator's decision and Sponsor's recommendation.
 
Patients with unresolved toxicities lasting 4 weeks or longer will not be permitted to continue on study.

LLN is the Lower Limit of Normality of the value reported in each evaluation performed at local laboratory of each investigational site.

The severity of the above mentioned events will be graded according to NCI Common Terminology Criteria for AE (CTCAE v. 4.03, 14th June 2010).

Patients with unresolved toxicities lasting 4 weeks or longer will not be permitted to continue on study.

In order follow the evolution of the observed abnormalities up to its stabilization and/or normalization (i.e. event resolved to at least Grade 1 or baseline values) and also to provide sufficient data to make dose adjustment decisions, **it is strictly recommended to perform additional study visits at least on bi-weekly basis upon occurrence of the following toxicities:**

- Grade 1 thrombocytopenia (i.e. PLTs count $<$ local LLN but $\geq 75 \times 10^9/L$);
- Grade 1 anemia (i.e. Hb value $<$ local LLN but ≥ 10 g/dL),
- ANC $< 2.0 \times 10^9/L$;
- Grade 2 non-haematological toxicities;
- Any SAE (if feasible).

In addition, additional study visits at least on weekly basis **should be performed** upon occurrence of the following toxicities:

- Grade ≥ 2 thrombocytopenia (i.e. PLTs count $< 75 \times 10^9/L$);
- Grade ≥ 2 anemia (i.e. Hb value < 10 g/dL),
- ANC $\leq 1.5 \times 10^9/L$;
- **Drug-related** Grade ≥ 3 non-haematological toxicities;
- **Drug-related** SAE (if feasible).

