4.3.3.2.2 Dose increase for inadequate efficacy in **Part B**

In **Part B**, the initial dose of Givinostat will be the MTD defined in **Part A** (i.e. 100 mg b.i.d.).

Based on evaluations performed as part of the visit procedures of the Day 28 of each Cycle up to the Cycle 5 (i.e. Cycle 1 Day 28, Cycle 2 Day 28, Cycle 3 Day 28, Cycle 4 Day 28, Cycle 5 Day 28) and/or in any necessary additional study visit, the Givinostat doses have to be decreased in case of the occurrence specific toxicities (see [paragraph 4.3.3.2.1](#)).

After a dose reduction, dosing may be restarted and then increased following recovery of the observed toxicity(ies) to controlled levels. The objective for restarting and then escalating after a reduction for safety reasons is to find the highest safe dose regimen of Givinostat for each patient that is necessary to obtain a clinico-haematological response, with increase in dose not more than the MTD defined in **Part A** (i.e. 100 mg b.i.d.).

After a dose reduction and in order to optimize the response for each individual patient avoiding specific drug-related toxicities, the Givinostat dosage **may be increased** for patients who meet all the following criteria, based on evaluations performed as part of the visit procedures of the Day 28 of each Cycle up to the Cycle 5 (i.e. Cycle 1 Day 28, Cycle 2 Day 28, Cycle 3 Day 28, Cycle 4 Day 28, Cycle 5 Day 28):

1. Inadequate efficacy as demonstrated by one or more of the following points:
 - a) HCT $\geq 45\%$, **or** HCT $< 45\%$ but at least 1 phlebotomy performed after the first 3 weeks of treatment, **or** HCT $< 45\%$ but at least three point higher than the HCT obtained at baseline (i.e. HCT at baseline (in %) plus at least a value of 3%), **or**
 - b) WBCs count $> 10 \times 10^9/L$, **or**
 - c) PLTs count $> 400 \times 10^9/L$, **and**

2. PLTs count > local LLN, **and**
3. Hb value \geq 12 g/dL, **and**
4. ANC \geq 1.5 x 10⁹/L.

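### The Grade 3 haematological row of Table 3 (Part B) fixes the restart dose without regard to the dose at onset, so it leaves open an unchanged dose from 75 mg b.i.d. and a step up from 50 mg b.i.d.

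*Protocol*

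**What the plan says.** Part B patients start at 100 mg b.i.d. and may receive 100, 75 or 50 mg b.i.d.; 50 mg b.i.d. is the lowest dose that can be dispensed (sections 4.3.3.2.1 and 4.4.1.1).

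The lead-in to Table 3 (section 4.3.3.2.1) makes a dose decrease obligatory "in case of the occurrence of at least one of the toxicities described in the Table 3". Section 4.3.3.2.2 repeats the duty: "the Givinostat doses have to be decreased in case of the occurrence specific toxicities".

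The rows of Table 3 treat patients whose dose has already been reduced in three different ways:

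- **Grade 1 and Grade 2 rows:** a separate bullet leaves these patients to case-by-case judgement: "For patients that are receiving a reduced daily dose of 75 mg b.i.d. or 50 mg b.i.d., daily dose must be evaluated".
- **Grade 3 haematological row:** immediate stop, at least one week off drug, recovery to at least Grade 1 or baseline, and exit if the toxicity is unresolved at 4 weeks. Then: "Daily dose has to be restarted at 75 mg b.i.d. or 50 mg b.i.d", chosen by the Investigator after discussion with the Sponsor. There is no split by dose at onset.
- **Grade 4 row:** the dose is left open: "The continuation of the study - and the study drug dosage - should be evaluated based on the" Investigator's decision and the Sponsor's recommendation.

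Increases have their own rules. Section 4.3.3.2 allows them after a reduction only for "inadequate efficacy at the reduced dosage in absence of specific toxicities". Section 4.3.3.2.2 treats restart and increase as successive steps ("dosing may be restarted and then increased following recovery of the observed toxicity(ies) to controlled levels"). Table 4 requires inadequate efficacy together with "PLTs count > local LLN", Hb of at least 12 g/dL and ANC of at least 1.5 x 10⁹/L.

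**The concern.** The restart pair suits a patient who had the event on 100 mg b.i.d., because both doses are then reductions. It does not suit a patient already reduced, and the plan creates such patients by design: the Grade 1 row obliges a step from 100 to 75 mg b.i.d. for mild thrombocytopenia, and the Grade 2 row can lead to 50 mg b.i.d. Thrombocytopenia is named among the most common adverse events of this drug (section 1.4), so a Grade 3 event on a reduced dose is foreseeable.

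Two things are at stake. A patient may be returned to the dose that preceded a Grade 3 event when a lower one is available. And sites may handle the same case differently, because the row and the surrounding rules point in different directions.

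**Working it through.** The plan states no figure on this point, so there is none to reproduce. The check compares every Part B dose at onset with each restart dose named in the Grade 3 row.

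**Inputs.** Possible Part B doses (section 4.4.1.1): 100, 75 and 50 mg b.i.d., that is 200, 150 and 100 mg/day. Restart doses (Table 3, Grade 3 row): 75 or 50 mg b.i.d., that is 150 or 100 mg/day.

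**Formula.** Change = (restart daily dose − onset daily dose) / onset daily dose.

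| Dose at onset | Restart at 75 mg b.i.d. | Restart at 50 mg b.i.d. |
|---|---|---|
| 100 mg b.i.d. | −50/200 = −25% | −100/200 = −50% |
| 75 mg b.i.d. | 0/150 = 0% | −50/150 = −33% |
| 50 mg b.i.d. | +50/100 = +50% | 0/100 = 0% |

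Three onset doses times two restart doses give six combinations: three decreases, two unchanged, one increase.

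**Reading the three that are not decreases against the other rules.**

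1. *75 to 75 mg b.i.d.* Sections 4.3.3.2.1 and 4.3.3.2.2 require a decrease, and 50 mg b.i.d. is available. The row leaves the unchanged dose open, so the rules conflict.
2. *50 to 75 mg b.i.d.* Restart needs recovery only to Grade 1 or baseline. Section 4.3.3.2.1 defines Grade 1 thrombocytopenia as platelets below the local LLN but at least 75 x 10⁹/L, and Grade 1 anaemia as Hb below the local LLN but at least 10 g/dL. A patient with platelets in that range, or with Hb from 10 to just under 12 g/dL, could restart under the row but would fail Table 4. Grade 1 thrombocytopenia is also itself a Table 3 toxicity, whereas section 4.3.3.2 allows increases only in the absence of such toxicities. Again the rules conflict.
3. *50 to 50 mg b.i.d.* No lower dose can be dispensed in Part B. This follows from the floor and is not a fault of the row.

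**After the fix below.** Four combinations remain: 100 to 75, 100 to 50, 75 to 50 and 50 to 50 (or discontinuation). None is an increase, and the only unchanged one is at the floor.

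**The case against.** The best defence is that the row is silent about reduced patients and names no such combination. It can be read as written for the 100 mg b.i.d. starting dose, with the rest of section 4.3.3.2 filling the gap. The parent section makes reductions *or interruptions* mandatory, and the row does order an interruption. The step from 50 to 75 mg b.i.d. is already restrained by section 4.3.3.2 and Table 4. The Grade 1, 2 and 4 rows do not force a decrease in reduced patients either, so tightening Grade 3 alone would leave the Grade 4 row laxer for the worse event. There are real safeguards: the stop, the week off drug, recovery, Sponsor discussion, the 4-week exit, at-least-weekly visits for Grade 2 or higher thrombocytopenia or anaemia, and the Investigator's power to withhold drug at any time (section 4.3.3.3). Section 1.4 also calls adverse events generally mild to moderate and reversible.

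Much of this stands. The safeguards limit the harm, the Table 4 restraint is genuine, and the point about the Grade 4 row has to be met in the fix. But an interruption satisfies only the parent section, not the duty to decrease stated twice below it. The Grade 1 and 2 rows at least address reduced patients and leave their dose to judgement; the Grade 3 row uses mandatory wording and confines the choice to two doses with no ceiling. That another section forbids what a row leaves open is a conflict to remove, not a reason to keep it.

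A reader might infer that the row *requires* an increase for Part B patients on 50 mg b.i.d. It does not: 50 mg b.i.d. is one of the two options. A reader might also count 50 to 50 mg b.i.d. as a breach of the duty to decrease; with no lower dose to give, it is not a mistake in the row.

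**Conclusion.** The defect holds, within limits. The Grade 3 restart rule ignores the dose at onset and so conflicts with other stated rules in two of its six combinations: 75 to 75 mg b.i.d. (0% against a required decrease; −33% is available) and 50 to 75 mg b.i.d. (+50% against the limits on increases). It is a correctable inconsistency in a safety table and deserves amendment.

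The conclusion rests on taking the row's wording literally and on the three Part B doses in section 4.4.1.1. The protocol gives no rate of Grade 3 events on a reduced dose, so no number of affected patients is claimed. The Simon two-stage figures do not depend on this rule, and it would be wrong to infer that the sample size, error rates or primary analysis are compromised.

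**What to change.** Split the restart sentence of the Grade 3 row by dose at onset:

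- from 100 mg b.i.d.: restart at 75 or 50 mg b.i.d. (unchanged);
- from 75 mg b.i.d.: restart at 50 mg b.i.d.;
- from 50 mg b.i.d.: restart at no more than 50 mg b.i.d., or discontinue, by Investigator decision after discussion with the Sponsor.

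Add to both the Grade 3 and the Grade 4 rows: *The restart dose must be below the dose at onset where a lower dispensable dose exists and is never above it; later increases only under Table 4.* Putting it in both rows keeps the Grade 4 rule from being looser than the Grade 3 rule.

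Keep the duty to decrease in sections 4.3.3.2.1 and 4.3.3.2.2. Add only an exception for patients already at the lowest dispensable dose and for the case-by-case bullets of the Grade 1 and 2 rows.

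The cost is an amendment to two table rows and two sentences, with no new visits, assessments or capsule strengths. The downside is slightly lower dose intensity for patients on 75 mg b.i.d. at onset, which Table 4 can reverse once its criteria are met.

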**Table 3 - Dose reduction rules in Part B (continue)**

Observed values/data	Action
Grade 4 thrombocytopenia (i.e. PLTs count $\leq 25 \times 10^9/L$) or Grade 4 anemia (i.e. life-threatening consequences; urgent intervention indicated) or Grade 4 febrile neutropenia (i.e. life-threatening consequences; urgent intervention indicated) or Grade ≥ 3 unmanageable toxicity	
Immediate temporary discontinuation of the treatment with Givinostat.
 
The treatment will be interrupted for at least one week. Anyway, the treatment for each new cycle will be delayed until the observed toxicity that is clearly not related to disease progression, has resolved to at least Grade 1 or the patient's baseline value.
 
The continuation of the study - and the study drug dosage - should be evaluated based on the Investigator's decision and Sponsor's recommendation.
 
Patients with unresolved toxicities lasting 4 weeks or longer will not be permitted to continue on study.

LLN is the Lower Limit of Normality of the value reported in each evaluation performed at local laboratory of each investigational site.

The severity of the above mentioned events will be graded according to NCI Common Terminology Criteria for AE (CTCAE v. 4.03, 14th June 2010).

Patients with unresolved toxicities lasting 4 weeks or longer will not be permitted to continue on study.

In order follow the evolution of the observed abnormalities up to its stabilization and/or normalization (i.e. event resolved to at least Grade 1 or baseline values) and also to provide sufficient data to make dose adjustment decisions, **it is strictly recommended to perform additional study visits at least on bi-weekly basis upon occurrence of the following toxicities:**

- Grade 1 thrombocytopenia (i.e. PLTs count $<$ local LLN but $\geq 75 \times 10^9/L$);
- Grade 1 anemia (i.e. Hb value $<$ local LLN but ≥ 10 g/dL),
- ANC $< 2.0 \times 10^9/L$;
- Grade 2 non-haematological toxicities;
- Any SAE (if feasible).

In addition, additional study visits at least on weekly basis **should be performed** upon occurrence of the following toxicities:

- Grade ≥ 2 thrombocytopenia (i.e. PLTs count $< 75 \times 10^9/L$);
- Grade ≥ 2 anemia (i.e. Hb value < 10 g/dL),
- ANC $\leq 1.5 \times 10^9/L$;
- **Drug-related** Grade ≥ 3 non-haematological toxicities;
- **Drug-related** SAE (if feasible).

Of note, the lowest dosage of Givinostat that can be dispensed to the patients in **Part B** is 50 mg b.i.d., i.e. a dosage that has been previously shown to be well tolerated. Of note, patients will self-administer daily Givinostat capsules at home at morning and at the evening (i.e. after 12 hours) with fluids and between meals (i.e. to take the study drug at least 2 two hours after the last meal, or no less than 1 hour before the meal).

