4.1.1.1 Definition of Dose Limiting Toxicity (DLT)

Dose Limiting Toxicity (DLT) is defined as the following **drug-related** toxicity:

- Grade 4 haematological toxicities, **or**
- Grade 3 febrile neutropenia, **or**
- Grade ≥ 3 non-haematological toxicities with exception of:
 - a) Grade 3 diarrhoea without adequate supportive care lasting less than 3 days, **and**

- b) Grade 3 nausea **or** vomiting without adequate supportive care lasting less than 3 days, **or**
- Any drug-related SAE, **or**
 - Any toxicity that is clearly not related to disease progression or intercurrent illness requiring interruption of dosing for more than 3 days during the first cycle.

The severity of the above mentioned events will be graded according to NCI Common Terminology Criteria for AE (CTCAE v. 4.03, 14th June 2010).

Only Dose Limiting Toxicities (DLTs) experienced during the first cycle of treatment will be considered for dose escalation decisions. DLTs include all AEs that are clearly **not** related to disease progression or intercurrent illnesses.

Patients who didn't experience a DLT and missed more than 10% of the doses in Cycle 1 of *Part A* will be replaced (see [paragraph 4.6.4](#)).

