4.1.1.5 Definition of MTD

If 2 or more patients per dose level experience a DLT, dose escalation will terminate and the MTD is the next lower dose level if no more than one out of 6 patients had a DLT at that level. Once all patients enrolled in *Part A* have been treated for at least 1 cycle, the study team will determine the MTD to be used in *Part B* based on the safety and tolerability profile of Givinostat observed as well as the PK and PD data, if applicable.

No intra-patient dose escalation will be permitted prior to determining the MTD.

At that time, patients on treatment at lower dose levels may be allowed to escalate their Givinostat dose up to the MTD for the remainder part of the study (**Part A**) at the discretion of the Investigator **and** after the written authorization of Italfarmaco S.p.A.. Of note, patients initially dosed at lower dose levels that are allowed to escalate their Givinostat dose up to the MTD for the remainder part of the study (**Part A**), will follow the dose modification rules of **Part B** (see [paragraph 4.3.3.2](#)). Total daily dose may never exceed the MTD defined in **Part A** (i.e. 100 mg b.i.d.).

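### Part B Table 3 names neutropenia only when febrile, so afebrile Grade 4 neutropenia not judged unmanageable requires no dose action at onset

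*Protocol*

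**What the plan says.** Section 4.3.3.2 makes Part B reductions or interruptions mandatory for specific toxicities. Section 4.3.3.2.1 then fixes which ones: the dose has to come down "in case of the occurrence of at least one of the toxicities described in the Table 3".

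Table 3 is strict on platelets. Even Grade 1 thrombocytopenia carries the instruction "Total daily dose must be reduced of 50 mg/die". Neutropenia appears in two rows, each time tied to fever: "Grade 3 febrile neutropenia" in the third row and "Grade 4 febrile neutropenia (i.e. life-threatening consequences; urgent intervention indicated" in the fourth. The fourth row also holds Grade 4 thrombocytopenia, Grade 4 anaemia and any toxicity of Grade 3 or higher that is unmanageable. Its action is immediate interruption for at least one week and until recovery to Grade 1 or baseline, after which continuation and dose rest on the investigator's decision and the sponsor's recommendation.

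In Part A, section 4.1.1.1 lists drug-related "Grade 4 haematological toxicities" as dose-limiting, and Grade 3 febrile neutropenia as a separate item. Section 4.3.3.1 adds: "Treatment for each new cycle will be delayed until dose limiting toxicities that are clearly not related to disease progression have resolved" to Grade 1 or baseline. Section 4.1.1.5 moves some Part A patients to the Part B rules, namely "patients initially dosed at lower dose levels that are allowed to escalate their Givinostat dose up to the MTD".

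**The concern.** A rule that names a closed list of mandatory triggers should not leave out a Grade 4 cytopenia that the same protocol treats as dose-limiting elsewhere. For neutropenia, Table 3 orders a stop only once fever is present or someone calls the event unmanageable, a word the protocol does not define. Two sites with the same afebrile Grade 4 result could both comply while one interrupts and the other continues 100 mg b.i.d. with weekly visits. What is at stake is patient safety and consistent conduct across sites.

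**Working it through.** The plan states no figure on this point, so the check is a reading of each rule against one case: Grade 4 neutropenia, no fever, not judged unmanageable.

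**Table 3, row by row (section 4.3.3.2.1)**

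| Row | Triggers | Does the case meet it? |
|---|---|---|
| 1 | Platelets below local LLN but at least 75 x 10^9/L | No, platelets only |
| 2 | Grade 2 thrombocytopenia; Grade 2 anaemia; non-haematological toxicity of Grade 3 or higher, with exceptions | No, the event is haematological and concerns neither platelets nor Hb |
| 3 | Grade 3 thrombocytopenia; Grade 3 anaemia; ANC below 1.0 x 10^9/L with fever | No, fever is required |
| 4 | Grade 4 thrombocytopenia; Grade 4 anaemia; Grade 4 febrile neutropenia; unmanageable toxicity of Grade 3 or higher | No, fever is absent and unmanageable is excluded by the case |

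No row applies, so no mandatory action follows at onset.

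**Other Part B rules that reach the case**

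- Section 4.3.3.2.1, below Table 3: ANC at or below 1.5 x 10^9/L should lead to weekly extra visits. This is monitoring, not a dose action.
- Section 4.3.3.2.2: a dose increase needs ANC of at least 1.5 x 10^9/L. This blocks an increase but does not lower the dose.
- Section 4.3.3.3: the investigator may withhold drug at any time for safety. This is permission, not a requirement.
- The sentence below Table 3 on toxicities unresolved for 4 weeks or longer names no row. Read broadly, it removes the patient from study, but only 4 weeks on.

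**Part A, same event, if drug-related**

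- Section 4.1.1.1: it is a DLT, with or without fever.
- Section 4.3.3.1: each new cycle waits for recovery to Grade 1 or baseline. This is the firm element.
- Section 4.3.3.1 on dose: patients may have up to two modifications, and "The first dose modification should be one dose level below the current dose". The wording permits and advises; it does not compel.

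**Patients who change rule sets.** The Amendment 2 rationale reports 3 Part A patients on 150 mg/day, below the MTD of 2 x 100 = 200 mg/day. At most these 3 could have moved to the Part B rules; whether any did is not stated. For such a patient the mandatory cycle delay would lapse as the dose rises.

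**Frequency.** The protocol gives no rate. As an illustration only, with an assumed per-patient risk r, the chance of at least one afebrile Grade 4 neutropenia among n patients is 1 - (1 - r)^n:

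- n = 28 (both stages): r = 0.01 gives 1 - 0.99^28 = 0.25; r = 0.02 gives 1 - 0.98^28 = 0.43.
- n = 12 (stop after Stage 1): r = 0.01 gives 1 - 0.99^12 = 0.11; r = 0.02 gives 1 - 0.98^12 = 0.22.

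These are upper bounds on the chance of meeting the gap, because some events would be called unmanageable.

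**Price of closing the gap.** Three cycles of 28 days are 84 dosing days to Cycle 3 Day 28. The minimum interruption is 7 days, and 7/84 = 8.3%.

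**The case against.** The best defence is that ANC was considered and given monitored discretion. The Amendment 2 rationale says the Part B rules were rewritten from Part A and earlier data. ANC thresholds trigger visits and block increases, and section 4.3.3.3 lets the investigator do whatever safety needs. The stated haematological concern is platelets. Entry requires WBC above 10 x 10^9/L and excludes ANC below 1.2 x 10^9/L. The only Cycle 1 DLT among 6 patients at 100 mg b.i.d. was dyspepsia. This stands as a reason to expect few events. It does not close the gap, because the same discretion exists for Grade 4 thrombocytopenia and anaemia and the protocol still made interruption mandatory there.

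The comparison with Part A also has limits. A reader might infer that Part A orders an immediate stop and a firm one-level reduction for this event. It does not: immediate interruption in section 4.3.3.1 is likewise reserved for unmanageable toxicity, and the reductions are worded permissively. At 100 mg b.i.d. the Part A scheme is in Figure 3, which is not visible in the text at hand. What remains is the DLT status and the mandatory delay of each new cycle.

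A reader might also infer that nothing but discretion protects the patient. That goes too far, since the 4-week sentence below Table 3 can be read as a mandatory stop that covers this event. It acts late, so the point about onset is unaffected.

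**Conclusion.** The gap is real and narrow. Under the current text, afebrile Grade 4 neutropenia not judged unmanageable requires no dose action at onset in Part B. That is inconsistent with mandatory interruption for the other two Grade 4 cytopenias in the same row, and with the DLT definition and cycle delay in Part A. It is a hole in a stated safety rule rather than detail left for another document.

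Its size cannot be taken from the protocol. A reader might suppose a per-patient risk of 5% or 10%, which would make a case in 28 patients likely, but nothing in the document supports such rates and the entry WBC criterion points the other way. No effect on power or error rate follows. This is a cheap improvement, not a threat to the trial's conclusions.

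**What to change.** In the Grade 4 row of Table 3, after the febrile entry, add: *or Grade 4 neutropenia (CTCAE v4.03), with or without fever*. Keep the row's action unchanged. Add one line: *if two rows apply, the more severe row governs*, because a Grade 4 count with fever can also meet the Grade 3 febrile entry. No separate ANC cut-off is needed, since the protocol already adopts CTCAE v4.03 grading.

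Leave the 4-week sentence below Table 3 as it is; limiting it to the interruption rows would narrow a safety rule in the less protective direction. Lower-grade afebrile neutropenia can stay under the present discretion and visits.

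Cost: an affected patient loses at least 7 of 84 dosing days (8.3%) to Cycle 3 Day 28, the minimum already imposed for Grade 3 and 4 thrombocytopenia or anaemia. No patients or visits are added: the differential count is already taken at every Day 28 visit, and low ANC already prompts weekly visits. The amendment may be substantial under section 8.1, which would require competent authority authorisation and a favourable ethics opinion before use.
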